1.3 Clinical Data to Date

Multiple studies demonstrate the safety and efficacy of pregabalin for neuropathic pain related to diabetic neuropathy, post herpetic neuropathy, spinal trauma, post-operative pain, restless leg syndrome, cervicobrachialgia, lumbosciatalgia, and neuropathic cancer pain [19]. One prospective single-arm study of 28 children who were given pregabalin for chemotherapy associated neuropathic pain demonstrated long-lasting pain relief in 86% of patients, with minimal side effects [20].

Version 06-01-2015 Page 10 Gabapentin, which has a similar chemical structure and appears to have a similar mechanism of action related to binding of the $\alpha 2$ - δ subunit of voltage sensitive calcium channel channels, has been used previously at this institution with retrospective analysis suggesting a possible decreased need for opioids in managing mucositis pain in patients undergoing radiation therapy to the head and neck [16].

1.4 Dose Rationale and Risk/Benefits

The recommended dose of pregabalin ranges from 150 mg/day to 600 mg/day divided into twice or three times daily doses. Increasing dose above 300 mg/day appears to correlate with increasing side effects including dizziness, somnolence, blurry vision, peripheral edema, and constipation. It appears that incremental benefits in neuropathic pain are smaller at the higher dose levels.

2 Study Objectives

Primary Objective

To assess the effectiveness of pregabalin in decreasing the cumulative dose of opioid used in the management of mucositis pain related to radiation therapy to the head and neck.

Secondary Objectives

To assess for quality of life and level of mucositis pain among subjects treated with pregabalin in conjunction with radiation therapy to the head and neck.

To compare the effects of pregabalin in decreasing the need for and degree of opioid use, quality of life, and level of mucositis pain in these patients.

3 Study Design

3.1 General Design

This will be a Pilot study - single institution, two-arm, randomized, double blind study. Eligible study subjects will be enrolled among those being treated for mucosal head and neck squamous cell cancer receiving definitive or post-operative radiation therapy (photons or protons) and concurrent platinum-based chemotherapy in the Department of Radiation Oncology at the University of Pennsylvania. All study subjects will receive pregabalin or matching placebo starting the 1st day of radiation therapy and stopping upon resolution of acute mucositis pain following completion of therapy, approximately one month after the completion of radiation therapy. If it is not feasible to start pregabalin or matching placebo anytime following the 1st day of radiation treatments, patients may start pregabalin or matching placebo anytime following the 1st day of radiation treatment up through the end of the 2nd week of radiation treatment, so long as the patients still meet all eligibility criteria in Sections 4.2 and 4.3.

E		R ^a	
Ν		А	Arm 1 ^b
R		Ν	pregabalin target dose 300mg/day
0	Concurrent Chemo	D	starting concurrent with RT
L		Ο	-
L		Μ	Arm 2 ^b
М		Ι	Placebo
E		Ζ	starting concurrent with RT
Ν		Е	-
Т			

Version 06-01-2015 Page 11 a) Patients will be randomized prior to starting pregabalin or matching placebo on 1st day of radiation treatment. Patients may also start pregabalin or matching placebo anytime following the 1st day of radiation treatment up through the end of the 2nd week of radiation treatment, so long as all eligibility criteria in Sections 4.2 and 4.3 are still met.

b) See section 5.2 for details of treatment regimen

Follow-up – approximately 1 month post completion of radiation treatments for all study subjects

3.2 Duration of Subject Participation

The subject participation will start with the recruitment and informed consent process in the time period prior to starting RT and will extend until initial follow-up one approximately (1) month after completion of RT. It is anticipated that total participation will be for three or four months.

3.3 Sequence and Duration of Trial Stages

We anticipate this trial to accrue approximately 2-4 subjects per month. This would result in a total duration of approximately 6-11 months for complete accrual. Patient treatment will last approximately 7 weeks, with an approximate one month follow-up on study. This would result in a total duration of approximately 9-14 months completion of the entire trial including accrual and follow-up.

3.4 Primary Study Endpoints

Total opioid use as recorded at weekly on-treatment visits and follow-up visit. Patients will keep a diary of opioid use at home during the week. The diary will be collected by the staff and recorded at the weekly visit.

3.5 Secondary Study Endpoints

QOL as self-reported at baseline, weekly on-treatment visits, and at follow-up visit.

Radiation induced mucositis (RIM) pain as self-reported at weekly on-treatment visits and at one month followup visit using the validated mouth and throat soreness score and overall mouth and throat soreness score as well as the short form Brief Pain Inventory (BPI).

3.6 Primary Safety Endpoints

Toxicity will be physician/NP reported at weekly on-treatment visits and at follow-up visit, and will be scored according to NCI CTCAE v4.02 [21]

4 Subject Selection and Withdrawal

4.1 Inclusion Criteria

- 1. Patients with a histologically confirmed diagnosis of mucosal head and neck squamous cell cancer receiving definitive or post-operative radiation therapy (photons or protons) and concurrent platinum-based chemotherapy at the University of Pennsylvania.
- 2. Age at least 18 years old.
- 3. Treatment entails significant risk for symptomatic mucositis likely to require opioid analgesia, as per the discretion of treating physician/NP.
- 4. Subjects are capable of giving informed consent. There are no exceptions to exclusion. The DSMC will not approve exceptions.

CONFIDENTIAL

4.2 Exclusion Criteria

- 1. History of hypersensitivity to pregabalin or gabapentin.
- 2. History of seizure or currently taking anti-epileptic medication.
- 3. Creatinine clearance < 30 mL/min by Cockcroft-Gault estimate.

CLCr = [140 – age(years)] x weight (kg) (x 0.85 for female patients)

72 x serum creatinine (mg/dL)

- 4. Has another painful condition requiring chronic use of opioid analgesic, gabapentin, or pregabalin.
- 5. History of serious mood disorder or attempted suicide as determined by patient's history and physical and by using the Depression Screening (Appendix H). Subjects with a score of greater than 10 or those answering #5 with scores greater than a "0" will be deemed ineligible to be enrolled on study .
- 6. History of angioedema.
- 7. New York Heart Association class III or IV heart failure.
- 8. Platelets < 150 mg/dL or history of thrombocytopenia.
- 9. The patient has any uncontrolled intercurrent illness including but not limited to psychiatric illness/social situations that would limit compliance or interfere with their ability to participate.

4.3 Subject Recruitment and Screening

Subjects will be recruited by physician/NPs or other health care professionals in the Department of Radiation Oncology clinical practices of the University of Pennsylvania. No inducements or coercion will be used.

Employees or students of the University of Pennsylvania will be eligible to enroll on this study provided all inclusion criteria are met and no exclusion criteria are identified. For these potential study subjects, additional safeguards to ensure that they are not subjected to potential coercion or undue influence will include a clear discussion that their study participation will not otherwise influence their standing at the University of Pennsylvania and that an alternative to study participation is to not participate and to receive otherwise standard treatment as recommended by their physician/NP. Additional effort will be undertaken to ensure that the handling of PHI (patient health information) for such study subjects will comply with HIPAA guidelines as outlined below.

4.3.1 Vulnerable Populations

Children, pregnant women, fetuses, neonates or prisoners are not included in this research study. Women of childbearing potential must be non-pregnant and non-lactating and willing to exercise an effective form of birth control during radiation therapy (e.g. oral contraceptive, IUD, condoms or other barrier methods etc.). Before receiving chemoradiation, female patients must have a negative pregnancy test. Hysterectomy or menopause must be clinically documented.

Early Withdrawal of Subjects

When to Withdraw Subjects

- 1. At the subject's request.
- 2. Determination by the investigator that it is no longer safe for the subject to continue therapy.
- 3. The presence of CTCAE Grade 4-5 toxicity possibly, probably or definitely related to the study drug.

How to Withdraw Subjects

1. If pregabalin has not been administered, the study subject will proceed to receive the recommended RT.

2. If pregabalin has been administered, the study subject will taper the dose gradually over a minimum of one week at the discretion of the treating physician/NP.

Data Collection and Follow-up for Withdrawn Subjects

Even though subjects may be withdrawn prematurely from the study, it is imperative to collect at least survival data on such subjects throughout the protocol defined follow-up period for that subject (though careful thought should be give to the full data set that should to be collected on such subjects to fully support the analysis). Such data is important to the integrity of the final study analysis since early withdrawal could be related to the safety profile of the study drug. If a subject withdraws consent to participate in the study:,

- If the patient withdraws consent, s/he will be given the choice of withdrawing completely meaning no further contact or data collection or giving the research team permission to follow up contact for data collection. It must be a high priority to try to obtain at least survivial data on all subjects. Patients that agree to be followed with be asked to sign to sign the 'Consent to Follow up' form (appendix G).
- If the PI, treating oncologist or physician withdraws the patient for any reason, the patient will be given the same choice as subjects who withdraw consent themselves. Patients agreeing to be followed with also sign the 'Consent to follow up.'
- If the patient is lost to follow up, the research study staff will make three documented attempts to confirm the subject's status. We would only use the contact information provided by the patient to our department as is our Standard of Practice.

5 Study Drug

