5.2 Treatment Regimen

Study subjects will self-administer oral preparation of pregabalin or matching placebo in twice daily dosage. Study subjects may use capsule form or solution, depending on medical necessity.

All study subjects will start taking 75mg of pregabalin nightly starting on the first day of radiation treatments. The dose will be increased to 75mg twice daily on day 3 and subsequently to 150mg twice daily on day 5.

Study subjects randomized to the treatment arm will continue to take 150mg of pregabalin twice daily for the duration of their radiation treatments until approximately their one month follow up visit. Subjects will be instructed at their follow up visit on how to taper the study drug.

Subjects randomized to the placebo arm will receive capsules and/or liquid that looks identical to the treatment arm. Subjects will titrate and taper in a fashion identical to the treatment arm.

At the discretion of the treating physician/NP, the interval between increasing dosage may be prolonged to a maximum of 4 days or the dosage reduced after the goal dose has been reached. Participants reporting excessive sedation or dizziness will be allowed to delay dose escalation. If a patient is not able to reach or maintain the goal dose at any point during the study (such as due to an adverse event at least possibly related to the study drug), the patient may continue on study and will be included in the analyses. The dose reached/dose

CONFIDENTIAL

Page 14

reduction will be recorded by the treating physician/NP with annotation of the rationale for the decision to maintain at that dose.

During titration, patients will be assessed daily by designated study staff before or after their daily radiation treatment in order to discuss/report with/to the PI any adverse events associated with the study drug.

Patients will be screened for suicidal ideation by designated study staff at baseline, daily during week 1 titration of the study drug and on a weekly basis during the study period until chemotherapy and radiation therapy are completed. Patients will be screened for depression again at the 1 month inspection visit. All patients will be screened using the Depression Screening assessment (appendix H).

Patients scoring a 10 or higher or reporting anything other than a 0 on question # 5 will meet with a physician/NP and will be:

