1. Immediately removed from the study and discontinue the drug using the taper schedule outlined in section 8.1 (renal dose tapering).

2. Urgently referred to the counseling service at the Abramson Cancer Center.

3. Escorted to PEEC (Psychological Emergency Evaluation Center) if a patient reports suicidal thoughts and a plan to commit suicide that they intend to carry out.

Subjects who develop 1) grade 3 or GREATER thrombocytopenia; or 2) experience an unanticipated event (such as those outlined in the pregabalin package insert) will be directed to reduce their dose by 50% starting that day. The subject will then decrease the study drug by 1 pill per day thereafter until complete discontinuation. Patients titrating over the weekends will be directed to call the Radiation Oncologist on call if they experience any new side effects.

Approximately four weeks following completion of radiation treatments, study subjects will taper the pregabalin dose for a minimum of one week before stopping. This taper will follow a reverse schedule of the titration: 75mg twice daily for three days, 75mg once a day for three days, then no medication on the seventh day. The rate of taper may be modified by the PI or treating physician/NP as per the subject's clinical situation and PI or physician/NP's discretion.

Study subjects with persistent mucositis pain responding to pregabalin may continue to take the pregabalin for up to 4 additional weeks on study. After this point, any additional pregabalin administration will be off-study and solely at the discretion of the treating physician/NP. At that time, the cost of the medication will become the responsibility of the patient (or their medical insurance).

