6.4 Follow up Visit

During the routine approximate one-month inspection follow-up visit, the subject will complete the OMQ, pain assessment, the Depression Screening and the quality of life questionnaire. The pain diary will be collected for the corresponding time frame. The physician/NP or designee will complete the toxicity assessment form with the subject. This visit will occur approximately 4 weeks post completion of the final radiation treatment, but may occur no less than 3 and no more than 6 weeks post completion of radiation treatment.

Version 06-01-2015 6.5 Schedule of Events

Study Procedures

				Follow up
	Eligibility	Baseline	Weekly during treatment	(approximately 1 month)
Tests and Laboratory				
History and PE	Х			
CBC and blood chemistry panel	X*		Х	
Assessments				
Depression Screening Form		Х	Х	X
Quality of Life Questionnaire		Х	Х	X
Pain Assessment Form		Х	Х	X
Toxicity Assessment Form/Adverse Events		X**	Х	Х
Oral Mucositis Questionnaire (OMQ)			Х	X
Pain Diary			Х	X
Study Drug				
Study drug dispensing			X***	X****
Pill Diary/Study drug compliance			Х	X

*with 30 days prior to eligibility check

** must be completed within 4 weeks of start of Pregabalin or matching placebo treatment

*** starting on first day of radiation treatment (or if applicable – starting any day following the first radiation treatment up through the end of the second week of radiation treatment)

****as needed to begin study drug taper

7 Statistical Plan

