7.2 Design

This is a 2 arm *double blind* randomized pilot trial to generate preliminary data on the cumulative opioid dose for head and neck cancer patients treated with either placebo (the control arm) or Lyrica (pregabalin). To reduce bias in terms of initiation of opioid treatment and dosage prescribed, neither the patient, the study coordinator, nor the treating physician/nurse practitioner will know whether Lyrica or placebo had been assigned to a patient. The cumulative opioid dose over an 11 week observation period will be recorded. Randomization will eliminate selection bias and balance patient factors between arms. Ten patients will be enrolled on each arm for a study total of 20 patients. Study drug will be taken daily during the approximately 7 weeks of radiotherapy and for 4 additional weeks post-radiotherapy. The primary choice of the opioid drug for this study is oxycodone.

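### The birth-control condition ends with radiation therapy, but study drug continues for nominally about 5 more weeks, and longer with the optional extension

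*Combined protocol and SAP*

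**What the plan says.** Section 4.3.1 keeps pregnant women and fetuses out of the study. It requires women of childbearing potential to be neither pregnant nor breastfeeding, with a negative pregnancy test before chemoradiation. Its only continuing preventive measure is that they be "willing to exercise an effective form of birth control during radiation therapy".

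Dosing is described elsewhere, and it runs past RT:

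- Section 7.2: "Study drug will be taken daily during the approximately 7 weeks of radiotherapy and for 4 additional weeks post-radiotherapy".
- Section 5.2, taper: "Approximately four weeks following completion of radiation treatments, study subjects will taper the pregabalin dose for a minimum of one week before stopping". The schedule is "75mg twice daily for three days, 75mg once a day for three days, then no medication on the seventh day", and "The rate of taper may be modified by the PI or treating physician/NP".
- Section 5.2, timing: "Subjects will be instructed at their follow up visit on how to taper the study drug". Section 6.4 says this visit "may occur no less than 3 and no more than 6 weeks post completion of radiation treatment", and the Section 6.5 schedule allows drug to be dispensed there for the taper.
- Section 5.2, extension: patients whose mucositis pain persists and responds to drug "may continue to take the pregabalin for up to 4 additional weeks on study".

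Section 3.1 ties stopping to resolution of acute mucositis pain, at about one month after RT. Section 8.1 reports adverse events until 30 days after the final dose and counts a birth defect as serious. Section 1.2.2.2.1 reports that pregabalin crosses the placenta and reaches milk in rats.

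**The concern.** The condition is tied to the wrong event. RT is background treatment that patients would receive anyway. Pregabalin is the exposure that the trial adds, and it outlasts RT. A site following Section 4.3.1 literally would hold a participant to birth control for the RT weeks only, while she may still be on blinded pregabalin.

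Nothing else in the visible text fills the gap. The only pregnancy test named comes before chemoradiation, and the schedule of events lists none. The withdrawal reasons do not name pregnancy. Adverse-event reporting does extend past the last dose, but it detects a problem and does not prevent one. It also shows that the protocol can anchor a safety period to dosing when it chooses to.

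What is at stake is a safeguard for individual participants. The sample size, the endpoints and the descriptive analysis are untouched.

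**Working it through.** This is timeline arithmetic, so no statistical formula applies.

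**Inputs.** RT lasts about 7 weeks and post-RT dosing 4 weeks (Section 7.2). The taper takes at least 1 week, with 3 + 3 = 6 dosing days as scheduled, and the optional extension is up to 4 weeks (Section 5.2). The visit window is 3 to 6 weeks after RT (Section 6.4). Drug may start as late as the end of RT week 2 (Section 3.1).

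**Reproducing the plan's own figure.** The Study Summary gives about 10 to 12 weeks of administration.

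- Start on RT day 1: 7 + 4 + 1 = 12 weeks.
- Start at the end of RT week 2: (7 − 2) + 4 + 1 = 10 weeks.

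The stated range therefore matches 4 weeks of post-RT dosing plus a one-week taper.

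**Planned dosing after RT, outside the birth-control condition.** The formula is weeks from end of RT to the visit, plus any extension, plus the taper. It assumes that the taper, or the extension, starts at the visit.

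| Case | Visit at 3 weeks | Visit at 4 weeks (nominal) | Visit at 6 weeks |
|---|---|---|---|
| No extension | 3 + 1 = 4 weeks | 4 + 1 = 5 weeks | 6 + 1 = 7 weeks |
| Days to last scheduled taper dose, no extension | 21 + 6 = 27 | 28 + 6 = 34 | 42 + 6 = 48 |
| Full extension, taper inside it | 3 + 4 = 7 weeks | 4 + 4 = 8 weeks | 6 + 4 = 10 weeks |
| Full extension, taper after it | 3 + 4 + 1 = 8 weeks | 4 + 4 + 1 = 9 weeks | 6 + 4 + 1 = 11 weeks |

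The last two rows are both shown because the protocol does not say whether the taper counts within the extension.

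**Share of planned dosing.** Nominally 5 of 12 weeks (42%) fall outside the condition, or 5 of 10 (50%) for the latest permitted start. Four of those five weeks come before the taper, at the target dose unless it has been reduced.

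**Narrowest reading.** Section 7.2 taken alone, with no taper, still leaves 4 weeks.

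**The case against.** The strongest objection is that the consent form is not in the material available and may already carry wider contraception instructions. It goes to the ethics board with the protocol (Section 11). This stands: the finding shows a fault in the protocol text and cannot show that patients go uninstructed. If the consent form is wider, Section 4.3.1 should be brought into line with it.

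Second, the clause is a condition of willingness. Nothing tells a woman to stop contraception when RT ends, and two of the listed methods, oral contraceptives and an IUD, are not naturally confined to the RT weeks. That also stands. The weeks above are weeks not covered by the wording, which is different from weeks of unprotected exposure.

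Third, the exclusion of pregnant women has no time limit, and the investigator may withdraw a patient on safety grounds. Both help, but neither prevents a pregnancy during post-RT dosing.

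Fourth, the longer figures are inferences. Section 5.2 also places the taper at about four weeks after RT, and no passage says outright that drug continues to week 6. The 11-week figure stacks the latest visit, the full extension and a taper after it. For a day-1 starter that means 7 + 11 = 18 weeks of drug, beyond the 10 to 12 weeks in the Study Summary and slightly beyond the three or four months of participation in Section 3.2. The nominal 5 weeks is the firmest figure. The others show what the text permits.

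Finally, the documents contain no evidence of fetal harm, only transfer in rats. That is right, and none is claimed here. The protocol has already decided to require birth control; the question is only when the requirement ends.

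**Conclusion.** The concern holds. The protocol states a birth-control rule whose end point falls before the end of study drug. The shortfall is nominally 5 weeks, roughly 4 to 7 across the visit window, and 7 to 11 with the full extension.

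These are planned durations, and they are neither risks nor firm bounds. They assume a one-week taper that starts at the follow-up visit, or after an extension counted from that visit. Drug may stop earlier if pain resolves, and the clinician may change the taper rate. Few women of childbearing potential are likely among the 20 patients (an assumption, since the documents give no figure), and 10 of the 20 receive placebo. Small numbers reduce how often the gap matters. They do not close it for a woman who falls into it. The change should be made, although nothing in the analysis depends on it.

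**What to change.** In Section 4.3.1, replace the RT-only period with: during radiation therapy and through the last on-study dose of study drug, including taper and any extension. Add the same condition to the Appendix A eligibility checklist, which as supplied has no pregnancy or birth-control line. Check the consent form and amend it if it repeats the RT-only wording.

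The cost is one phrase, one checklist line and possibly a consent edit. For the few women affected, the commitment lengthens by nominally 5 weeks, roughly 4 to 7, and by up to about 11 with the full extension. Design, sample size and analysis stay as they are.
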